Scarce literature is available regarding the utility of CEUS to help differentiate imaging findings of more aggressive RCCs versus less aggressive ones. This study will aim to use CEUS to evaluate the quantitative and qualitative imaging features of RCC prior to surgical removal, and to correlate these features with pathologic grade following surgery. We hypothesize that tumors with different pathologic grades will show different patterns of qualitative enhancement, as well as different perfusion kinetics. If findings on CEUS do correlate with pathologic grade, CEUS could possibly add additional information to the clinical decision making process, separately or in addition to biopsy at the discretion of the clinical team.

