Items to be documented from the medical record, radiologic studies (CEUS and prior imaging), and surgical and pathologic records include age, sex, indication for each radiologic study, pertinent results of prior radiologic studies, time interval from RCC clinical diagnosis to surgery, CEUS quantitative findings (peak signal intensity, time to peak, area under the curve, mean transit time, of both the mass and normal renal tissue), CEUS qualitative findings (description of enhancement pattern), pertinent surgical findings, and pathologic findings including grade.

This study will monitor for adverse events (as defined below) related only to the injection of and/or physiologic reaction to Lumason. Available data shows that reactions to Lumason are rare, with the most common reactions being headache, nausea, and dizziness. True allergic reactions (ranging from hives and urticaria to anaphylactoid reactions) are even less common. Patients will be monitored by study personnel during and for at least 30 minutes after intravenous injection of contrast for immediate reactions. The patients will also be given instructions to call with any concerns in the 48 hours following contrast injection.

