#### Determining Attribution to the Investigational Procedure

Attribution: An assessment of the relationship between the AE and the study intervention. CTCAE does not define an AE as necessarily “caused by a therapeutic intervention”. After naming and grading the event, the clinical investigator must assign an attribution to the AE using the following attribution categories:

Relationship	Attribution	Description
Unrelated to investigational agent/intervention	Unrelated	The AE is clearly NOT related
	Unlikely	The AE is doubtfully related
Related to investigational agent/intervention	Possible	The AE may be related
	Probable	The AE is likely related
	Definite	The AE is clearly related

Descriptive statistics will be performed, documenting total number of patients with each item above, and comparing numbers for different pathologic grades, where pathologic grades 1 and 2

and pathologic grades 3 and 4 will be combined for inferential analysis. We will analyze how each item varies with pathologic grade using students t-test (continuous variables) and Fisher's test (categorical variables). With 40 subjects enrolled, we expect to see approximately 20 grade 1/2's and 20 grade 3/4's. At least 12 subjects per group is considered sufficient for a pilot study (ref: Julius SA. Sample size of 12 per group rule of thumb for a pilot study. *Pharmaceutical Statistics*. 2005;4(4):287–91.).

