## **Enrollment**

This is a pilot study to determine whether there is evidence that CEUS findings have correlation with pathologic staging. There has been almost no prior work done in this area and we do not have data to support sample size and power calculations. We propose imaging 40 patients because the cost of 40 Lumason doses is what we can reasonably expect to be reimbursed by our department. If we have promising results, we expect to apply for an industry or federal grant to study CEUS in a much larger population of patients with renal tumors, either at IU alone or together with other centers.

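### For two-category items, Fisher's test is valid but conservative at this sample size; Boschloo's exact test would recover roughly 4 to 9 points of power on average at no cost in patients

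*Combined protocol and SAP*

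**What the plan says.** The statistical paragraph sits at the end of the section on determining attribution. It pools grades 1 and 2, "and pathologic grades 3 and 4 will be combined for inferential analysis", and tests each recorded item by "students t-test (continuous variables) and Fisher's test (categorical variables". It names no variant of Fisher's test. On group sizes it says "With 40 subjects enrolled, we expect to see approximately 20 grade 1/2's and 20 grade 3/4's".

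The Rationale expects "different patterns of qualitative enhancement, as well as different perfusion kinetics" across grades, so categorical items carry part of the hypothesis. The Methods list "CEUS qualitative findings (description of enhancement pattern" among the items to record, without naming categories or saying how many there are.

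The Enrollment section sets 40 patients by the cost of contrast doses and says "we do not have data to support sample size and power calculations". The plan states no significance level, sidedness, effect size or feature rate.

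**The concern.** Fisher's test conditions on both margins of the table. Here the number of tumours showing a given feature is not fixed by design. With about 20 per group, that conditioning leaves few attainable p-values, so the rejection rate under no association falls well short of the nominal level. The unused error rate is lost power.

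The study exists to look for evidence of association, and its size is capped by budget. Power lost through the choice of test cannot be bought back with patients, but it can be recovered by naming another exact test. At stake is a real difference in a yes/no feature being missed more often than necessary.

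**Working it through.** **Inputs.** Test, grade grouping and expected group sizes: the statistical paragraph. Loss of non-RCC or ungraded tumours after imaging: exclusion criterion 4. Assumed, because the documents give none: two-sided 5% level, feature rates p1 and p2, and a two-category item. The plan has no power figure to reproduce.

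**Why Fisher's test is conservative: one margin by hand.** Suppose 17 of 40 tumours show a feature, with 20 per group. The probability that x of the 17 fall in the first group is C(20,x)·C(20,17−x)/C(40,17), where C(40,17) = 88,732,378,800.

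- 5/20 v 12/20: the terms for x = 0 to 5 sum to 2,375,853,480. Doubling for the symmetric tail gives p = 4,751,706,960 / 88,732,378,800 = 0.0536.
- 4/20 v 13/20: dropping the x = 5 term (15,504 × 125,970 = 1,953,038,880) leaves 422,814,600. Then p = 845,629,200 / 88,732,378,800 = 0.0095.

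No attainable p-value lies between these, so at this margin a 5% test rejects with probability 0.95%. Boschloo's p-value for 5/20 v 12/20 is 0.030.

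**True size.** Over all tables with a of n1 and b of n2 showing the feature, the rejection probability is

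Σ Bin(a; n1, p1)·Bin(b; n2, p2)·1[test rejects].

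Size is the maximum of this with p1 = p2. Boschloo's test takes Fisher's p-value as its statistic. It rejects up to the largest cut-off that keeps the maximum at or below 5%. Fisher's own cut-off of 0.05 already satisfies that condition, so Boschloo's test rejects every table that Fisher's does.

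| Split | Fisher, maximum size | Boschloo, maximum size |
|---|---|---|
| 20/20 | 2.53% | 4.64% |
| 19/21 | 3.44% | 4.83% |
| 18/22 | 3.28% | 4.46% |
| 17/23 | 2.99% | 4.59% |
| 16/24 | 3.23% | 4.77% |
| 17/19 | 3.66% | 4.91% |
| 12/12 | 2.28% | 4.49% |

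**Power (%), Fisher then Boschloo.** Gains are taken from unrounded values. The last column averages over a Binomial(40, 0.5) split, restricted to groups of at least 12 (99.4% of the probability).

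| Assumed rates | At 20/20 | Gain | Averaged over split | Gain |
|---|---|---|---|---|
| 10% v 40% | 49.2, 60.9 | 11.7 | 51.8, 57.9 | 6.1 |
| 20% v 50% | 40.9, 49.2 | 8.3 | 43.4, 49.4 | 6.0 |
| 30% v 60% | 34.7, 44.7 | 9.9 | 37.4, 46.0 | 8.6 |
| 10% v 50% | 74.2, 82.2 | 7.9 | 76.2, 80.3 | 4.1 |
| 20% v 60% | 65.0, 72.8 | 7.8 | 67.1, 73.5 | 6.5 |
| 30% v 70% | 59.9, 70.5 | 10.6 | 62.5, 71.2 | 8.6 |

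Exactly 20/20 has probability C(40,20)/2^40 = 12.5% under that model, so the averaged column is the fairer summary. Fisher's size averaged over the split is at most 3.15%.

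**Where the gain is smaller.**
- At 19/21, with the 10% rate in the group of 19, 10% v 40% goes from 55.7 to 56.6, a gain of 0.9. In the same arrangement 5% v 25% gains nothing (34.7 under both tests).
- At 17/19 the gains are 3.5 (20% v 60%), 3.5 (30% v 70%) and 5.1 (10% v 40%).
- Large differences leave little to gain even at 20/20: 5.5 for 20% v 70% and 3.2 for 10% v 60%.

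**More than two categories.** At 20 v 20 the Fisher-Freeman-Halton test reaches a size of about 4.5% with three categories and 4.7 to 4.8% in the four-category cases tried. Little is lost there.

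**The case against.** Fisher's test is a conventional, valid choice, and whether to condition on the margins is a long-standing matter of judgement. The study is a pilot that claims no power, so the plan breaks no promise of its own. Many items are tested without multiplicity control, and some conservatism per item has value in that setting. All of this stands, and it is why the point is an improvement and not a defect. It does not defeat the change: the alternative holds the same nominal level and is never less powerful at it. If stricter control is wanted, a stated adjustment is better than conservatism that shifts with the split.

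Three stronger readings are tempting but not supported:

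- **That the true size is at most 2.5% and the loss 7 to 12 points.** This belongs to exactly 20 v 20 and selected 30- to 40-point differences. The plan says only "we expect to see approximately 20 grade 1/2's and 20 grade 3/4's", and grade is known only after surgery. Neighbouring splits give sizes of 3.0 to 3.7% and often smaller gains.
- **That the enhancement-pattern part of the hypothesis is held to a stricter standard than the kinetic part.** The Rationale says "tumors with different pathologic grades will show different patterns of qualitative enhancement", but nothing says pattern is a two-category item. With three or four categories the shortfall largely disappears, and the fix would leave that test unchanged.
- **That the plan misstates its error rate.** It states no significance level, so there is no stated rate to contradict.

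**Conclusion.** For two-category items the planned test is valid but conservative, with a maximum true size of 2.5% at exactly 20 v 20 and about 3.0 to 3.7% at nearby splits. For assumed differences of 30 to 40 points, the cost against Boschloo's test is roughly 4 to 9 points of power averaged over a random split of 40. It can approach nothing at particular splits and rates.

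The conclusion rests on a two-sided 5% level, assumed feature rates and, for the averaged figures, an even chance of either grade group. It holds if exclusions reduce the number analysed: averaged gains were about 2 to 8 points at a total of 36, 5 to 7 at 32 and 6 to 10 at 28. It does not extend materially to items with three or more categories. This is a worthwhile, low-cost efficiency improvement, not an error or contradiction in the plan.

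**What to change.** In the statistical paragraph, state a two-sided 5% level. Specify Boschloo's exact unconditional test for items with two categories, and the Fisher-Freeman-Halton test for items with more than two unordered categories. Say in advance which items fall in each class; for enhancement pattern this means listing the categories before grade is known.

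The cost is a sentence or two of analysis wording and standard software, with no added patients or data. The downside is that the maximum false-positive rate per two-category item rises from about 2.5 to 3.5% to about 4.5 to 4.9%, still within 5%. Because several items are tested without multiplicity control, the plan should also say that these results are exploratory.

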## **Data monitoring**

CEUS is an inherently low-risk procedure when performed in centers with expertise. IU has been one of the leaders in the USA in studying the use of CEUS since it was approved by the FDA. We will have a data safety committee composed at minimum of the PI, a listed investigator urologist and radiologist, and another radiologist not involved in the study. The committee will meet after the first five patients have completed the renal CEUS to monitor accrual, workflow, any issues affecting recruitment and patient safety, data acquired thus far, and any new research impacting the study. The study will also collect adverse event details, including defined adverse events of interest, timeframe for collection, etc.

Primary data will be collected via direct data capture from measurement instrument and stored electronically in REDCap. The storage location will be backed up automatically. Quality assurance steps will include testing of database by study team prior to moving to production mode. The following quality control methods will be used: single entry with random checks of accuracy and extraction and cleaning of data that will be used for analysis quarterly.

This study will be conducted in accordance with the IU Simon Cancer Center Institutional DSMP for **Low Risk Trials**.

Investigators will conduct continuous review of data and subject safety. **Quarterly review meetings** for low risk trials are required and will include the principal investigator, clinical research specialist and/or research nurse (other members per principal investigator's discretion). **Quarterly** meeting summaries should include review of data, the number of subjects, significant toxicities as described in the protocol, and responses observed. Study teams should maintain meeting minutes and attendance for submission to the DSMC upon request.

### **Data and Safety Monitoring Committee**

The IUSCC Data and Safety Monitoring Committee (DSMC) is responsible for oversight of subject safety, regulatory compliance, and data integrity for this trial. The DSMC will review this study annually to review overall trial progress, toxicity, compliance, data integrity, and accrual per the Institutional DSMP.

Furthermore, the DSMC conducts an administrative review of serious adverse events (SAEs), deviations, reportable events, and any other outstanding business. Major issues may require further DSMC review or action.

At any time during the conduct of the trial, if it is the opinion of the investigators that the risks (or benefits) to the subject warrant early closure of the study, the DSMC Chair and Compliance Officer

must be notified within 1 business day via email, and the IRB must be notified within 5 business days. Alternatively, the DSMC may initiate suspension or early closure of the study based on its review.

### **Study Auditing and Monitoring**

All trials conducted at the IUSCC are subject to auditing and/or monitoring per the Institutional DSMP. Reports will be reviewed by the full DSMC at the time of study review.

### **Data Management/ Oncore Reporting Requirements**

The DSMC reviews data and study progress directly from Oncore; therefore, timely data entry and status updates are vital. Study data must be entered within Oncore promptly, no later than one week from study visit occurrence. Subject status in Oncore will be updated in real time, as this may affect overall trial enrollment status. Global SAEs and deviations will be reviewed on a monthly basis by the DSMC Chair directly from Oncore.

### **Study Accrual Oversight**

Accrual data will be entered into the IU Simon Cancer Center OnCore system. The Protocol Progress Committee (PPC) reviews study accrual twice per year, while the PPC coordinator reviews accrual quarterly.

### **Oncore Safety Reporting**

In addition to protocol- and regulatory-required safety reporting, all serious adverse events (SAEs) will be captured in the Oncore system within 1 business day of notification. Initial SAE reporting will include as much detail as available, with follow-up to provide complete information. Attributions will be assessed to study drugs, procedures, study disease, and other alternate etiology.

### **Protocol Deviation Reporting**

Protocol deviations will be entered into OnCore within 5 days of discovery and reviewed by the DSMC Chair on a monthly basis. Findings will be reported to the full DSMC at the time of study review. For serious or repetitive protocol deviations, additional action may be required by the DSMC.

## **Enrollment**

This is a pilot study to determine whether there is evidence that CEUS findings have correlation with pathologic staging. There has been almost no prior work done in this area and we do not have data to support sample size and power calculations. We propose imaging 40 patients because the cost of 40 Lumason doses is what we can reasonably expect to be reimbursed by our department. If we have promising results, we expect to apply for an industry or federal grant to study CEUS in a much larger population of patients with renal tumors, either at IU alone or together with other centers.

## **Resources/Budget**

We have applied to our departmental project development team for funding for Lumason doses. A budget is under development. All other costs associated with CEUS, including imaging time

and the time of the investigators, will be the responsibility of the departments of Urology and Radiology and Imaging Sciences.

